4.4 Strategies for Recruitment and Retention

Case managers will inform the potential participants of the study and let them know that a study team member will contact them. Following referral by case management, eligible participants will be contacted by study staff via phone to provide the initial consent. Eligibility will be confirmed by the study personnel, and potential participants will be invited to participate in the study.

Subjects participating in this study will be compensated approximately \$25 for each research assessment (\$125 total) for completion of the study. Subjects will receive \$25 via check or gift card in the mail for remote visits. There is no charge or compensation for the weekly psychotherapy sessions.

If participants do not “log on” to the Prism system for 7 consecutive days, a study team member will call them to make sure they do not have questions, technical issues, or require re-training.

5. Registration Procedures

5.1 Subject Registration (WCM only)

Not applicable.

5.2 Subject Registration (Sub-sites)

Not applicable.

6. Data Reporting / Regulatory Considerations

6.1. Data Collection

6.1.1. Study outcomes: Feasibility and Acceptability

To evaluate acceptability and feasibility we will record the number of clients who are meet eligibility criteria and accept the intervention (versus refuse). Acceptability will be assessed based on client satisfaction with the therapy and the technology. The Clients Satisfaction Questionnaire will be administered at weeks 9 and 12 with benchmarks will be set at ≥ 3 (out of 4).

This will be recorded by the study team member who interviews the potential study participants. No personal information will be stored for ineligible persons or persons who do not consent to participate. Only descriptives regarding whether or not the person contacted was eligible and consented will be recorded. This will be recorded by the study team member performing recruitment using an online form.

6.1.2. Questionnaires (baseline and post-study)

Personnel conducting the study will verbally ask questions contained in the questionnaires described, and record the participants answers using pen/paper or electronic form. Study investigators will write the participant number on each questionnaire so questionnaires from the same participant can be matched. Assessments will be collected prior to the first Engage session and following the final Engage session.

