3.2.1 Baseline assessment and training

Participants will be mailed the Prism technology or provided the technology in-person. Participants will be provided a tablet and trained in the utilization of Prism by a study team member and technology specialist. Trainings will occur virtually (via Zoom or telephone) or in-person. In-person training will be conducted by research assistants and occur in the participants' home as many are homebound. The determination for in-person versus virtual training will be based on the preference of the participant the research regulations of Weill Cornell Medicine pertaining to the on-going COVID-19 pandemic. Following the training, baseline questionnaire data will be collected with the study team member reading the questions aloud and marking the responses of the participant. Included questionnaires are described in the subsequent section.

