3.2.2 Questionnaires

Questionnaires collected during the baseline and study assessments include (attached to IRB application):

1. Hamilton Depression Rating Scale (HAMD) for depression severity
2. Behavioral Activation for Depression Scale (BADS) for behavioral activation*
3. Duke social interaction subscale – to assess social connection
4. Duke perceived support subscale – to assess perceived social support
5. UCLA 3-item scale – to assess loneliness
6. 12-item World Health Organization Disability Assessment Schedule (WHODAS 2.0)- to assess different domains of disability**

7. Technology readiness questionnaire (Jay & Willis, 1992)*
8. Mobile Device Proficiency Scale (MDPQ-16)
9. Computer tablet opinions questionnaire (Czaja et al., 2018)*
10. Demographics**
11. Client Satisfaction Questionnaire 3-item for therapy satisfaction
12. Intent to Participate – to assess intention to continue study

*Pre and post only (i.e. not at 3, 6 or 9 weeks)

**Pre only

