4.3 Exclusion Criteria

1. Psychotic depression by SCID-V, i.e. presence of delusions
2. High suicide risk, i.e. intent or plan to attempt suicide in the near future
3. Presence of any Axis I psychiatric disorder or substance abuse other than unipolar major depression
4. History of psychiatric disorders, hypomania, are excluded
5. Acute or severe medical illness, i.e. delirium, metastatic cancer, decompensated cardiac, liver, or kidney failure, major surgery, stroke, or myocardial infarction during the three months prior to entry; or drugs often causing depression, e.g. steroids, reserpine, alpha-methyl-dopa, tamoxiphen, vincristine
6. Current involvement in psychotherapy
7. Cognitive impairment (i.e. telephone administered MoCA < 11)
8. Currently dwelling in non-community dwelling (e.g. prison, nursing home)
9. Hearing that would not allow participants to complete sessions with the RA/therapist
10. Vision impairment that would not allow the participant to use the study provided tablet
11. Inability to speak English
12. Aphasia interfering with communication
13. Literacy – assessed by reading a paragraph designed for those at 6th grade reading level

INSTRUMENTS	Administered by:	Screening	Baseline	Wk 3	Wk 6	Wk 9	Wk 12
Screening Assessment							
Demographic Questionnaire	Research Assistant (RA)	X	X				
Medication List	RA	X					
Health Information Questionnaire	RA	X					
Functional status (WHODAS 12-item)	RA		X			X	X
Telephone- MoCa	RA	X					
Dx, Depression Severity and Anhedonia							
Hamilton Depression Rating Scale (HAMD)	Research Assistant	X	X	X	X	X	X
Structured Clinical Interview for DSM -V	Clinician	X					
SCID Score Sheet	RA	X					
PHQ-9	Clinician						Weekly during clinician sessions
Behavioral Activation							
Behavioral Activation for Depression Scale (BADS)	RA		X	X	X	X	X
Social Connection and Loneliness							
Duke (social interaction and perceived support subscales)	RA		X	X	X	X	X
UCLA Loneliness Scale 3-item	RA		X	X	X	X	X
Technology							
Technology readiness questionnaire	RA		X			X	
Mobile Device Proficiency Scale (MDPQ-16)	RA		X			X	X
Computer Tablet Opinions Questionnaire	RA		X			X	
Other							
Client Satisfaction Questionnaire 3-item	RA			X	X	X	X

Intent to Participate	RA		X	X	X	X	

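### The only numeric acceptability benchmark (CSQ ≥3 of 4) is asked aloud by the staff role that also gives in-person Prism training, which is likely to raise scores by an unknown amount

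*Protocol*

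**What the plan says.** Acceptability is part of the primary aim (Protocol Section 1.1). Section 6.1.1 gives its basis: "Acceptability will be assessed based on client satisfaction with the therapy and the technology". The same section sets the threshold: "The Clients Satisfaction Questionnaire will be administered at weeks 9 and 12 with benchmarks will be set at ≥ 3 (out of 4". No other acceptability or feasibility measure has a numeric target. Uptake versus refusal is recorded without one, and the response and remission rates in the Data Analysis section are efficacy comparisons.

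The CSQ is item 11 in Section 3.2.2, listed as "Client Satisfaction Questionnaire 3-item for therapy satisfaction". Section 6.1.2 states how the listed questionnaires are given: "Personnel conducting the study will verbally ask questions contained in the questionnaires described, and record the participants answers". The schedule of instruments that follows the exclusion criteria names the research assistant (RA) as the person who administers the CSQ.

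On training, Section 3.2.1 names a study team member and a technology specialist, and adds: "In-person training will be conducted by research assistants". That training takes place in the participant's home. At baseline, a study team member reads the questionnaires aloud once training is over. Study team members also telephone anyone who has not logged on for 7 days (Sections 4.4 and 6.1.4).

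The exclusions in Section 4.3 include "Vision impairment that would not allow the participant to use the study provided tablet" and a reading check at 6th-grade level. Section 3.2.4 gives every participant a tablet with internet access.

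**The concern.** A satisfaction question put aloud by the team whose programme is being rated invites a courteous answer. Here the role that asks is also a role that teaches part of the intervention. The participants are older, depressed and selected for loneliness or isolation (Section 4.2), and some were trained at home. No section separates trainer from assessor, offers a private answer, or tells participants that the team will not see their individual ratings.

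Any upward shift goes into the one acceptability figure that is held against a threshold. The historical comparison covers response and remission only, so nothing in the design would reveal a shift in satisfaction. The SAP is now descriptive, so the result will be read as a mean against 3. According to Section 8.1, the study is meant to show whether a larger one is warranted.

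**Working it through.** **Step 1: is the role overlap in the text?**

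| Task | Who does it | Source |
|---|---|---|
| Asks and records the CSQ | Study personnel; RA in the schedule | Section 6.1.2; schedule |
| Prism training, any mode | Study team member and technology specialist | Section 3.2.1 |
| Prism training, in person | RAs | Section 3.2.1 |
| Calls after 7 days without log-on | Study team member | Sections 4.4, 6.1.4 |
| Engage therapy, weekly PHQ-9 | Clinician | Section 3.2.3; schedule |

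The RA role both trains (in person) and asks the CSQ. The clinician does not ask it.

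**Step 2: is reading aloud needed?** Vision and literacy are screened, and a tablet is supplied. Most enrolled participants should manage three items alone. Hand function is not screened, so this cannot be claimed for everyone.

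**Step 3: how large could the effect be?** The benchmark has no derivation to reproduce. The only planning figure is the sample size: 3 per month × 17 months = 51, consistent with the stated 50. The SAP calls the completed number small but does not give it, so n = 10 is also shown, as an assumption. The documents give no CSQ mean, SD or interviewer effect. They also do not say whether ≥3 applies to an item, a participant's average or the sample mean. The illustration takes it as the sample mean of item averages.

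With true mean μ, standard deviation SD and upward shift b:

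P(sample mean ≥ 3) = 1 − Φ((3 − μ − b) / (SD/√n))

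Example with μ = 2.8, SD = 0.6, n = 50, b = 0: the standard error is 0.6/√50 = 0.085, (3 − 2.8)/0.085 = 2.36, and the probability is 0.9%.

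All results for an assumed true mean of 2.8:

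| n | SD | no shift | +0.1 | +0.2 | +0.3 |
|---|---|---|---|---|---|
| 50 | 0.6 | 0.9% | 11.9% | 50% | 88.1% |
| 50 | 0.8 | 3.9% | 18.8% | 50% | 81.2% |
| 10 | 0.6 | 14.6% | 29.9% | 50% | 70.1% |
| 10 | 0.8 | 21.5% | 34.6% | 50% | 65.4% |

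**Step 4: when does it not matter?** Take n = 50 and SD = 0.8, so the standard error is 0.113. If the true mean were 3.5, the benchmark would be met without any shift: (3 − 3.5)/0.113 = −4.42, a chance above 99.9%. If it were 2.3, even +0.3 would not rescue it: (3 − 2.6)/0.113 = 3.54, a chance below 0.1%. The mode decides the result only when the true score is close to 3.

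**The case against.** Several points on the other side stand.

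- **Same person.** A reader might infer that each participant is questioned by the person who trained them. The documents show overlap by role only. Training may be virtual, and virtual training is not assigned to RAs by name.
- **Therapy satisfaction.** Section 3.2.2 labels the CSQ as a measure of therapy satisfaction, and the clinician who delivers therapy does not give it. That is a real separation. It leaves the conflict clearest for the technology, which Section 6.1.1 also counts.
- **Other evidence.** A reader might infer that acceptability rests on the CSQ alone. Uptake (Section 6.1.1), attendance and therapist satisfaction (6.1.3), logged Prism use (6.1.4) and the interviews (3.2.5) also inform feasibility and acceptability. Attendance and logged use do not depend on what a participant tells an RA. None of these has a threshold, however.
- **Control arm.** A control arm would not remove courtesy bias from an absolute benchmark, so its absence is not the fault.
- **Completion.** Reading aloud protects completeness in a frail, often homebound group. Tablet completion could lose answers from those struggling with the technology, who may be the least satisfied, and that would also bias scores upward. This is a genuine trade-off, and it is why a fallback is needed.
- **Timing.** The SAP refers to the resulting sample, so collection appears to be over.

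These points limit the claim but do not remove it. For most participants the protocol's own screening takes away the need to read three items aloud, and nothing in the text protects the answer from the presence of programme staff.

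**Conclusion.** The concern holds as a likely, unquantified upward bias on the only thresholded acceptability measure, arising from the mode of asking and from an overlap of roles. It is an avoidable weakness of design and not a contradiction in the plan.

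The upward direction is a judgement, and the size is unknown. With an assumed true mean of 2.8 and n = 50, a shift of 0.2 would move the chance of passing from 1-4% to 50%, and 0.3 would move it to 81-88%. At n = 10, the chance is already 15-22% with no shift and reaches 65-70% with 0.3. These figures rest on assumed means, SDs and shifts, and on reading ≥3 as a sample mean.

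A reader might go further and conclude that the reported CSQ result is inflated, or that any true mean slightly below 3 would be reported as a pass. The documents support neither. They give no CSQ data, and a shifted mean of exactly 3 passes only about half the time.

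**What to change.** At each CSQ visit, have participants complete the three items privately, on the study tablet or on a paper form in a sealed or return envelope. Tell them that the therapist, trainer and assessor will not see individual answers. The participant number already used on forms (Section 6.1.2) keeps records linked.

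Keep read-aloud as a fallback for anyone who asks for it or does not return the form, preferably done by a team member who did not train that participant. Record the mode, and report the benchmark overall and by mode. With small numbers the by-mode figures are descriptive only. State also whether ≥3 applies to an item, a participant's average or the sample mean.

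The cost is some protocol wording and a short form, with no extra staff. The downside is some missing or delayed forms, possibly among those who find the technology hard, which the fallback limits.

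If collection is already complete, report how the CSQ was administered, say where known whether the assessor had trained the participant, and qualify the benchmark result as possibly inflated.

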6.1.3. Expert assessment

Weekly depression severity is tracked using the PHQ-9 by the clinician. Each session, clinicians will also record when a new participant initiates therapy and whether or not the patient attends each therapy session using an online form.

Acceptability will be evaluated based on the client and therapist satisfaction participating in Engage-Prism using the Client Satisfaction Questionnaire (CSQ 3-item).

6.1.4. Technology utilization

The Prism system collects de-identified statistics regarding the frequency and duration of utilization of each of the Prism applications (e.g. calendar, web browser, classroom), but does not collect surveillance data such as message content or search history. The data is stored on a secure, encrypted server where only study team members will have access.

As described above, if participants do not “log on” to the Prism system for 7 consecutive days, a study team member will call them to make sure they do not have questions, technical issues, or require re-training.

6.1.5. Post-study Interviews

Interviews will be audio-recorded. The team member conducting the interview will take notes to supplement the recording. As feasible, audio recordings will be sent to a HIPAA-compliant, CITI-certified transcription service or transcribed by a study team member. Although participants will be instructed not to provide any PHI during the interview, the transcription service will omit PHI if it is accidentally verbalized by the participant. The transcripts and investigator notes will serve as the data to be analyzed related to the interviews. Audio recording and transcripts will be kept on a secure server that only study personnel have access to through password protected logins.

6.1. Data Analysis

Baseline, interim, and post-study assessment data will be analyzed using statistical hypothesis testing with appropriate parametric or non-parametric tests as dictated by the nature of the assessment output and the distribution of the data collected.

Technology utilization data will be analyzed and reported using aggregated descriptive statistics. Secondary analyses may involve comparing differences in time using the various applications included in Prism, and differences in use based on participant demographics.

Qualitative data from the follow-up interviews be analyzed using inductive methods and the constant comparative process. Coding will be accomplished by multiple coders using consensus coding to elicit key themes from the data.

We will conduct a comparison with a matched sample of case management clients obtained from our prior research project (R01 MH075900, PI - [name]; R01 MH075897, PI - [name]) .We will compare the Engage-Prism participants response and remission rates with the rates found in the CARE-D study. We expect equal response rates (33-42.5% and remission rates (31- 37.9%) ([name], 2016)

7. Regulatory Considerations

7.1. Institutional Review Board/Ethics Committee Approval

As required by local regulations, the Investigator will ensure all legal aspects are covered, and approval of the appropriate regulatory bodies obtained, before study initiation.

Before initiation of the study at each study center, the protocol, the ICF, other written material given to the patients, and any other relevant study documentation will be submitted to the appropriate Ethics Committee. Written approval of the study and all relevant study information must be obtained before the study center can be initiated or the IP is released to the Investigator. Any necessary extensions or renewals of IEC/IRB approval must be obtained for changes to the study, such as amendments to the protocol, the ICF, or other study documentation. The written approval of the IEC/IRB together with the approved ICF must be filed in the study files.

The Investigator will report promptly to the IEC/IRB any new information that may adversely affect the safety of the subjects or the conduct of the study. The Investigator will submit written summaries of the study status to the IEC/IRB as required. On completion of the study, the IEC/IRB will be notified that the study has ended.

All agreed protocol amendments will be clearly recorded on a protocol amendment form and will be signed and dated by the original protocol approving signatories. All protocol amendments will be submitted to the relevant institutional IEC/IRB for approval before implementation, as required by local regulations. The only exception will be when the amendment is necessary to eliminate an immediate hazard to the trial participants. In this case, the necessary action will be taken first, with the relevant protocol amendment following shortly thereafter.

Once protocol amendments or consent form modifications are implemented at the lead site, Weill Cornell Medicine, updated documents will be provided to participating sites. Weill Cornell Medicine must approve all consent form changes prior to local IRB submission.

Relevant study documentation will be submitted to the regulatory authorities of the participating countries, according to local/national requirements, for review and approval before the beginning of the study. On completion of the study, the regulatory authorities will be notified that the study has ended.

7.2. Ethical Conduct of the Study

The Investigators and all parties involved will conduct this study in adherence to the ethical principles based on the Declaration of Helsinki, GCP, ICH guidelines and the applicable national and local laws and regulatory requirements.

This study will be conducted under a protocol reviewed and approved by the applicable ethics committees and investigations will be undertaken by scientifically and medically qualified persons, where the benefits of the study are in proportion to the risks.

7.3 Informed Consent

Patients will provide verbal informed consent (script and information sheet attached).

7.2.4 Compliance with Trial Registration and Results Posting Requirements

Not applicable – not a clinical trial

7.2.5 Record Retention

Essential documents are those documents that individually and collectively permit evaluation of the study and quality of the data produced. After completion of the study, all documents and data relating to the study will be kept in an orderly manner by the Investigator in a secure study file. Essential documents should be retained for 2 years after study conclusion. In addition, all subjects' medical records and other source documentation will be kept for the maximum time permitted by the hospital, institution, or medical practice.

8. Statistical Considerations

8.1 Sample Size/Accrual Rate

The goal of this early-stage pilot feasibility study is to assess feasibility, acceptability and impact of a brief behavioral treatment for depression (Engage) combined with social support (Prism). Though we have planned statistical hypothesis testing for a comparison with a historical sample, our goal is not to demonstrate definitive significant differences or establish but understand whether this is a feasible, acceptable, promising intervention that warrants further exploration with a larger sample of participants. The sample size is based on previous work by the investigators in similar feasibility assessments of the Engage therapy ([name] et al., 2016).

9. Adverse Event Reporting Requirements

Not applicable, this is not a clinical intervention.

10. Unanticipated Problems Involving Risks to Subjects or *Others*

Not applicable

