1.1. Objectives

Our primary aim in this pilot project is to test the feasibility, acceptability and impact of a brief behavioral treatment for depression (Engage) combined with video social support (PRISM 2.0) among socially isolated/lonely case management clients who endorse depressive symptoms. Secondarily, we will assess technology-related outcomes.

We plan to recruit 50 subjects based on a proposed recruitment of at least 3 subjects per month (17 months). Eligible participants will be offered the combination of Engage and Prism 2.0, called Engage-Prism.

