3.2.3. Engage therapy sessions

Participants will complete **9 Engage therapy sessions**. Engage is a form of personalized, stepwise treatment for late-life depression. The main intervention of Engage is an adapted form of behavioral activation tailored to older adults focused on “reward exposure,” namely encouraging patients to engage in (i.e., expose themselves to) rewarding activities between sessions to enhance activation of the reward system. At each session, patients will be guided to select a rewarding activity they had not engaged in recently or wanted to do more often. Then, the clinician will help patients develop a plan to engage in the selected activity and to cope with potential difficulties when exposed to such rewarding situations. If a patient does not successfully engage in planned rewarding activities and show clinical improvement by the third session, the clinician will add techniques to address barriers to reward exposure (Solomonov et al, 2019). Weekly depression severity is tracked using the PHQ-9. Engage has previously demonstrated efficacy for decreasing depressive symptoms in older adults ([name] et al, 2016).

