4.2 Inclusion Criteria

Criteria Referral to study:

1. Age at least 60 years.
2. English speaking.
3. Currently enrolled in case management at in 2 included agencies
4. Major depression on the SCID and 24-item Hamilton Depression Rating Scale (HAM-D) ≥ 19
5. Report of loneliness social isolation as determined by the UCLA 3-item scale and Duke social interaction subscale, respectively

Following referral, participants must be willing and able to consent to the study procedures and related activities.

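### Protocol section 9 switches off adverse-event reporting for a reason the protocol itself contradicts, and neither document defines how harms are collected, reported or summarised

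*Protocol*

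**What the plan says.** Protocol section 9 (Adverse Event Reporting Requirements) reads, in full: "Not applicable, this is not a clinical intervention". Section 10 and its subsections 10.1 and 10.1.1, on unanticipated problems, are each marked not applicable, with no reason given.

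Elsewhere the protocol describes the intervention and its recipients as follows:

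- Section 1.1 gives the aim as to "test the feasibility, acceptability and impact of a brief behavioral treatment for depression (Engage"), combined with the PRISM 2.0 platform. Section 8.1, directly above section 9, repeats this description.
- Section 3.2.3: "Engage is a form of personalized, stepwise treatment for late-life depression". If a patient does not carry out the planned activities and "show clinical improvement by the third session, the clinician will add techniques to address barriers to reward exposure".
- Section 4.2 requires "Major depression on the SCID and 24-item Hamilton Depression Rating Scale (HAM-D) ≥ 19".
- Section 4.4 refers to the weekly contacts as psychotherapy.
- Section 4.3 excludes at entry "High suicide risk, i.e. intent or plan to attempt suicide in the near future".

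Two passages bear on safety in general terms. Section 7.1 obliges the investigator to tell the IRB without delay about new information that may affect participants' safety. Section 7.2 commits the study to GCP, ICH guidelines and applicable regulations.

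The SAP replaces the planned hypothesis tests with descriptive statistics, giving the mean and standard deviation as examples. It does not mention harms.

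**The concern.** A pilot may keep its harms plan short, but section 9 does something different. It sets a rule, that adverse-event reporting does not apply, and rests it on a statement of fact that the rest of the protocol contradicts. Staff who followed sections 9 and 10 would have no event definition, no collection point and no reporting route, while section 7.1 tells the investigator to report safety information promptly.

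What is at stake is the decision the pilot is meant to inform. Section 8.1 says the study should show whether the intervention merits work in a larger sample. If only benefit, satisfaction and uptake are defined as outcomes, that decision is taken without harms data, and a report with no events could be mistaken for a report of no harm. The participants have major depression and the treatment is aimed at it, so deterioration is an outcome a reader would expect to see counted.

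**Working it through.** The plan states no figure to reproduce on this point. The check is a comparison of passages, followed by a search of both documents for any harms procedure.

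**Step 1: is the reason in section 9 consistent with the rest of the protocol?**

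| Feature | Where | Consistent with section 9? |
|---|---|---|
| Behavioral treatment for depression whose impact is tested | 1.1, 8.1 | No |
| Stepwise treatment, adjusted by a clinician according to clinical improvement | 3.2.3 | No |
| SCID major depression with HAM-D of at least 19 | 4.2 | No |
| Weekly contacts called psychotherapy | 4.4 | No |

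No passage supports the statement that this is not a clinical intervention.

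**Step 2: is section 10 consistent with section 7.1?** An unanticipated problem involving risk to participants is an example of the information section 7.1 says must go to the IRB. Section 10 declares that topic, including its definition and reporting, not applicable. Both cannot govern.

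**Step 3: is there a harms procedure elsewhere?**

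- *Schedule of instruments (section 4.3).* It has 17 rows: demographics, medication list, health information, WHODAS, telephone MoCA, HAMD, SCID, SCID score sheet, PHQ-9, BADS, Duke, UCLA, technology readiness, MDPQ-16, tablet opinions, CSQ-3 and intent to participate. None is named for adverse events. The medication list and the "Health Information Questionnaire" are marked at screening only. This count is supporting evidence at most, because an event log need not appear in a table of instruments.
- *Measures that could reveal worsening or bad experiences.* HAMD is scheduled at screening, baseline and weeks 3, 6, 9 and 12. PHQ-9 is collected weekly in sessions. WHODAS is scheduled at baseline and weeks 9 and 12 (section 3.2.2 instead marks it as pre only). Section 3.2.5 adds a week-9 interview on barriers and facilitators. Section 6.1.3 records therapy initiation and attendance, and section 3.2.2 lists "Intent to Participate – to assess intention to continue study". None of these is designated as harms data.
- *Suicide risk.* It is an entry exclusion. No later measure is designated to record it as a harm.
- *Abbreviation list.* AE, SAE, SUSAR, DSMB and DSMP are listed, but no procedure uses them.
- *Analysis.* The Data Analysis section mentions response and remission rates but no count of worsening. The SAP does not mention those rates, so their status is unclear, and it specifies no harms summary.

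**Step 4: illustration only.** Suppose events had been collected systematically in n participants and none occurred. The one-sided 95% upper bound on the event risk is 1 − 0.05^(1/n):

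- n = 50 (planned, section 1.1): 1 − 0.05^(1/50) = 5.8%
- n = 30 (assumed): 9.5%
- n = 20 (assumed): 13.9%
- n = 10 (assumed): 25.9%

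The SAP gives no achieved N, so the last three are assumptions. Without systematic collection no such bound can be stated at any n. The finding does not rest on these figures.

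**The case against.** The strongest reply concerns reach and weight. Neither document makes a safety claim. The stated outcomes are feasibility, acceptability and impact, the analysis is now descriptive, and no planned estimate changes if section 9 is corrected. HAMD and PHQ-9 are repeated often enough to show deterioration, the week-9 interview could bring out negative experiences, and sections 7.1 and 7.2 carry general obligations. The SAP's reference to the resulting sample suggests that conduct may be over, which would leave only a limitation statement and a retrospective count.

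Much of this stands, and it limits what can be inferred. Three stronger readings are tempting, and the documents support none of them:

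- *That harms were not recorded in practice.* The questionnaires, interview script, consent script and information sheet are attachments not reproduced here. They may contain event items.
- *That worsening would go unreported.* The SAP offers the mean and standard deviation as examples, not as a closed list. A count of worsening is not specified, but it is not excluded.
- *That section 7.1 is the only passage bearing on safety conduct.* Section 7.2 also commits to GCP and ICH, although it sets out no procedure.

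The reply does not rescue section 9. The protocol does not argue that the study is low risk and needs only light harms reporting; it gives a different reason, which is incorrect. Section 7.1 requires information to be passed on but does not say what is gathered, when or by whom, and sections 9 and 10 point staff the other way.

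**Conclusion.** The concern holds. Section 9 is wrong as written: it is a rule resting on a reason that the protocol contradicts in sections 1.1, 3.2.3, 4.2, 4.4 and 8.1. Section 10 conflicts with section 7.1. Apart from that duty and the general commitment in section 7.2, neither document defines how harms are collected, reported or summarised.

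The consequence is bounded. Followed as written, the pilot could not treat an absence of reported events as evidence of safety or tolerability. A reader might go further and infer that the intervention is unsafe or that events were missed; the documents show neither.

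Confidence is high for the contradiction, which rests on text alone. It does not extend to what was collected in practice. The correction should be made before results are reported, because the statement is false, the population has major depression, and the remedy is cheap.

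**What to change.** 1. By dated amendment, or as a reported limitation if conduct has ended, correct the statement in section 9 and reconcile sections 9 to 10.1.1 with sections 1.1, 3.2.3, 4.2, 4.4, 7.1 and 7.2. Do not silently rewrite the text that governed the study.
2. If any participant is still in follow-up, record adverse events, serious adverse events and unanticipated problems on a short form at existing contacts, and report them as section 7.1 requires.
3. Add one descriptive SAP table over all enrolled participants. It should give known adverse and serious adverse events, and individual worsening from the HAMD and PHQ-9 scores already scheduled. State the definition of worsening, and label it post hoc if it is set after the data have been seen. If response and remission rates are shown alongside, say first whether they are still planned.
4. If collection is complete, label retrospective counts as such and state that harms were not systematically collected, so an absence of reported events is not evidence of safety.

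How clinicians act on events is for the study team.

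**Cost.** One amendment or limitation paragraph and one table. If follow-up continues, there are at most 9 sessions + 4 post-baseline assessments (weeks 3, 6, 9 and 12) = 13 short entries per participant, with no added visits. These fall in 10 distinct weeks (1 to 9, and 12), assuming one session in each of weeks 1 to 9. If collection is complete, the work is a record review of enrolled participants. Counting worsening needs no new measurements. The downside is a small amount of form or review work, and retrospective counts will be incomplete.
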